5. ANALYSIS POPULATION

5.1. All Treated Population

The all treated population will consist of all subjects who are enrolled into the study and received study treatment (IMP or CP). All treated population will be used in efficacy analyses.

5.2. Safety Population

The safety analysis set will consist of all subjects who are enrolled into the study and received study treatment (IMP or CP). Safety population will be used in safety analyses.

5.3. PK Population

All PK sub-study subjects with evaluable PK parameter data and no major protocol deviations with an impact on PK data will be included in the PK analysis set.

6. STATISTICAL ANALYSES

6.1. General Considerations

Descriptive statistics and analyses will be provided by cohort, the age groups within Cohort 2 and, where appropriate, overall (combined all cohorts). Descriptive statistics for continuous variables will include the number of observations, mean, standard deviation (SD), median, minimum, and maximum values. For categorical variables, summary measures will include the number and percentage of subjects in each category.

Individual subject data will be presented in listings by cohort, subject identification number (ID), treatment schedule and, where appropriate, assessment.

All data summaries and tabulations will be prepared by using SAS® Version 9.1 or later.

For the purpose of reporting, subject weights and doses are rounded to zero decimal place.

Safety analyses will be summarized by the CP Treatment Period and by IMP Treatment Period.

Unless specifies otherwise, the efficacy analyses will be presented for all subjects in the all treated population as follows:

- Cohort 1 only
- Cohort 2 only
- Each of the 3 age groups within Cohort 2
- Cohorts 1 and 2 combined

The primary efficacy analysis will be based on the separate analyses for Cohort 1 for adult population and Cohort 2 for pediatric population using all treated population.

Efficacy data will be summarized similarly for CP Treatment Period.

PK analyses will be summarized by 21- or 28-day cycles for the IMP Treatment Period, unless otherwise specified.

6.2. Interim Analysis

Two interim safety analyses will be performed to evaluate safety data from the first 15 subjects to receive the IMP before Group 3 begin receiving the IMP. The first interim analysis will be performed for Group 1 subjects (5 subjects) and the second interim analysis will be performed for Group 2 subjects (10 subjects).

In addition, there will be an interim analysis after the first 20 subjects in Group 3 have completed 6 months of IMP dosing to support a DSMB review.

No other interim analysis is planned. However, when all subjects in Cohort 1 have completed the LTSV, and all data have been fully reconciled, a database lock of Cohort 1 will occur in order to close out study sites. When all subjects in Cohort 2 have completed the LTSV, a CSR will be prepared for the entire data set.

6.3. Methods for Missing Data

If lab data are missing for a visit and a retest was performed, the retest values may be used for the associated visit.

No other data imputation will be used in the analysis of this study including the PK evaluations.

6.4. Visit Windows

Data will be summarized and listed using the recorded nominal visit values, regardless of the actual study day on which a value was collected.

7. SUBJECT ENROLLMENT AND DISPOSITION

7.1. Subject Disposition

Subject disposition information will be summarized for all subjects by cohort and by Treatment Period. Summaries will include: the number of enrolled subjects, the number of subjects in each analysis population, the number of subjects completing the study, the number of subjects who are ongoing (for interim analyses only), the number of subjects discontinuing the study and the primary reason for study discontinuation. Additionally, total number of enrolled subjects by site will be summarized and listed.

7.2. Protocol Deviations

All protocol deviations will be documented throughout the study and will be provided in a listing.

8. EVALUATION OF BASELINE MEASUREMENTS

8.1. Demographics and Baseline Characteristics

Demographic data will include date of birth, age (based on date of informed consent), gender, race, and ethnicity; baseline characteristics data will include weight, height, PIDD diagnosis type, time since first PIDD diagnosis, IgG dose level prior to study enrollment, baseline IgG trough level, and chest X-ray results. Demographic and baseline characteristic data will be summarized for age, gender, ethnicity, baseline weight, height, PIDD diagnosis type, years since first PIDD diagnosis, IGIV dose level prior to study enrollment, IGSC dose level prior

to study enrollment, baseline IgG trough level, and chest X-ray. Demographic and baseline characteristics data will also be listed.

8.2. Medical History

A complete medical history that include past surgeries during the past 2 years, SBIs documented in the last 5 years, and any previous adverse drug reactions (ADRs) will be obtained. Medical history data will be coded and will be summarized by system organ class (SOC) and preferred terms (PT).

All medical and surgical history data will be listed.

9. EVALUATION OF TREATMENT EXPOSURE AND COMPLIANCE

9.1. Exposure to Study Treatment

Subject exposure to the study drug (IMP or CP), displayed as total number of infusions received, number of infusions per subject, total average IGIV dose per infusion (mg/kg) received, total weeks on study drug, lot numbers of IMP, number of subjects completing ≥ 6 and 12 months of dosing, and total exposure time in years will be summarized and listed.

CP administered will be summarized by the following IGIV products:

- Gammaplex 5%
- Carimune 6%
- Gammagard Liquid 10%
- Gamunex-C 10%
- Octagam 10%
- Privigen 10%
- Octagam 5%
- Bivigam 10%
- Flebogamma 10%

Study drug administration data, including start and stop times and infusion rates, and treatment infusion interruption data for CP and IMP will also be provided in a listing.

9.2. Compliance to Study Drug

Subject compliance to study drug will be calculated as total volume administered (mL) divided by the total volume planned (mL), provided as a percentage. Compliance data for individual subjects will be provided in a listing and summarized using average compliance by subject.

10. EFFICACY ANALYSIS

10.1. Primary Efficacy Endpoint

The primary efficacy endpoint in this clinical study is the rate of clinically documented SBIs per subject during the 12-months study observation period. SBIs are defined as:

- Bacterial pneumonia
- Bacteremia and septicemia
- Osteomyelitis/septic arthritis
- Bacterial meningitis
- Visceral abscess

The rate of occurrence of such infections will be calculated for each subject as $52n/w$, where n is the number of reported SBIs and w is the number of weeks on study.

For the primary endpoint, a 99% one-sided (upper) confidence limit for the incidence rate of SBIs (scaled to represent 12 months exposure if necessary) will be derived, and the objective of demonstrating that the true SBI rate is below 1 per subject per year will be considered established if this upper limit is less than 1.

To calculate the confidence limit, a negative binomial regression model will be used. This model includes an overdispersion parameter to account for possible intra-subject correlation as well as the actual time period each subject is on the study as an offset variable.

The null hypothesis for this analysis is that the true SBI rate is at least 1 per subject per year, and the alternative hypothesis is that this rate is less than 1 per subject per year.

H0: the acute SBI rate ≥ 1.0 per person-year

H1: the acute SBI rate < 1.0 per person-year

Rejection of the null hypothesis is therefore equivalent to demonstration of the study objective to show that the true SBI rate is less than 1 per subject per year.

The proposed method of analysis makes appropriate allowance for any intra-subject correlation in the incidence of SBIs. Such correlation would occur whenever variability in the individual subject-specific SBI rates exceeds what would be expected in the presence of true Poisson variability. The proposed statistical test based on a negative binomial model includes an overdispersion parameter reflecting any such inflated variance.

No formal statistical analyses will be done comparing the primary efficacy endpoint between the CP Treatment Period and the IMP Treatment Period.

The following SAS code can be used.

```
proc genmod data = xx;  
  model count= /offset=logdur dist=poisson link=log dscale alpha = 0.02;  
  estimate 'estimate rate' intercept 1 / alpha=0.02;
```

ods output Estimates=Estimates;
run;

The primary efficacy analysis will be performed using all treated population for Cohort 1 only and for Cohort 2 only.

Additionally, the primary efficacy analysis will be repeated in the all treated population for each of the age groups within Cohort 2 and for Cohorts 1 and 2 combined. For the analysis within each of the age groups with Cohort 2, only point estimates will be provided. Their associated confident intervals will be suppressed due to limited number of subjects within each age group and no sufficient statistical power for the influential analyses.

In addition, a frequency table giving the number of subjects with 0, 1, 2 ... acute SBIs, a description of each acute SBI and summary statistics for the duration of SBI will be summarized.

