All subjects who are exposed to at least one dose of the IMP will be included in the safety analysis set. The primary efficacy analysis will be based on the all treated population analysis set, which will be identical to the safety set. In addition, a modified per-protocol population analysis set will be defined as only subjects who receive at least 6 infusions and provide data.

No data will be imputed.

Efficacy Analysis

Primary Efficacy Endpoint

For the primary endpoint, a 99% one-sided (upper) confidence limit for the incidence rate of SBIs (scaled to represent 12 months exposure if necessary) will be derived, and the objective of demonstrating that the true infection rate is below 1 per subject per year will be considered established if this upper limit is less than 1.

To calculate the confidence limit, a negative binomial regression model will be used. This model includes an over-dispersion parameter to account for possible intra-subject correlation as well as the actual time period each subject is on the study as an offset variable.

The null hypothesis for this analysis is that the true SBI rate is at least 1 per subject per year, and the alternative hypothesis is that this rate is less than 1 per subject per year. Rejection of the null hypothesis is therefore equivalent to demonstration of the study objective to show that the true rate is less than 1 SBI per subject per year.

The proposed method of analysis makes appropriate allowance for any intra-subject correlation in the incidence of SBIs. Such correlation would occur whenever variability in the subject-specific SBI rates exceeds what would be expected in the presence of true Poisson variability. The proposed statistical test is based on a negative binomial model that includes an overdispersion parameter reflecting any such inflated variance.

Subgroup analyses will be performed based on gender and region (USA, Russia).

Secondary Efficacy Endpoints

Secondary efficacy endpoints will be presented using the appropriate descriptive statistics and summarized according to treatment time periods (Waiting Period, IMP Treatment Period). No hypotheses will be tested.

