12.1 Analysis Populations

The safety analysis set will consist of all subjects who are enrolled into the study and received study product. The all treated population analysis set will be the same as the safety set. A modified per-protocol population analysis set will be defined as all subjects in the full all treated population set who remain in the study for at least 6 infusions.

A per-protocol (PP) analysis set will consist of all subjects in the all treated population set who complete the whole 12-month study period and who do not have any major protocol violations as described in the Data Handling Plan.

The analyses described below will be presented for all subjects in the all treated population, the modified PP population, and the PP population as follows:

- Cohort 1 only;
- Cohort 2 only;
- Each of the 3 age groups within Cohort 2;
- Cohorts 1 and 2 pooled.

The primary efficacy analysis will be based on the all treated population analysis set, with separate analyses for Cohort 1 and Cohort 2.

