12.3.2 Primary Efficacy Endpoint

The primary efficacy endpoint in this clinical study is the rate of acute serious bacterial infections (pneumonia, bacteremia and septicemia, osteomyelitis/septic arthritis, bacterial meningitis, visceral abscess) per subject during the 12-month study observation period while receiving IMP. Serious bacterial infections (SBIs) must be confirmed with the tests and outcomes as described in Section 21.1.

The rate of occurrence of such infections will be calculated for each subject as $52n/w$ where n is the number of reported infections and w is the number of weeks on study.

For the primary endpoint, a 99% one-sided (upper) confidence limit for the incidence rate of SBIs (scaled to represent 12 months exposure if necessary) will be derived, and the objective of demonstrating that the true infection rate is below 1 per subject per year will be considered established if this upper limit is less than 1.

To calculate the confidence limit, a negative binomial regression model will be used. This model includes an over-dispersion parameter to account for possible intra-subject correlation as well as the actual time period each subject is on the study as an offset variable. The null hypothesis for this analysis is that the true SBI rate is at least 1 per subject per year, and the alternative hypothesis is that this rate is less than 1 per subject per year. Rejection of the null hypothesis is therefore equivalent to demonstration of the study objective to show that the true rate is less than 1 per subject per year.

The proposed method of analysis makes appropriate allowance for any intra-subject correlation in the incidence of SBIs. Such correlation would occur whenever variability in the individual subject-specific SBI rates exceeds what would be expected in the presence of true Poisson variability. The proposed statistical test based on a negative binomial model includes an overdispersion parameter reflecting any such inflated variance.

No formal statistical analyses will be done comparing the primary efficacy endpoint between the Waiting Period and the IMP Treatment Period.

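### SAP 5.1, 5.2 and 10.1 are not aligned with the plan's own restriction of the primary SBI rate to time on IMP

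*SAP*

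**What the plan says.** **Analysis sets.** SAP 5.1, the population for the efficacy analyses, reads: "The all treated population will consist of all subjects who are enrolled into the study and received study treatment (IMP or CP". SAP 5.2 repeats the rule: "The safety analysis set will consist of all subjects who are enrolled into the study and received study treatment (IMP or CP". The protocol synopsis (general statistical approach) is narrower: "All subjects who are exposed to at least one dose of the IMP will be included in the safety analysis set"; it makes the all treated set identical to that safety set. Protocol 12.1 is looser: "The safety analysis set will consist of all subjects who are enrolled into the study and received study product". SAP 5 defines no IMP-treated set.

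**Numerator, time and offset.** SAP 10.1 defines the endpoint as the rate of "SBIs per subject during the 12-months study observation period". The subject rate is 52n/w, "where n is the number of reported SBIs and w is the number of weeks on study". The model allows for overdispersion "as well as the actual time period each subject is on the study as an offset variable". Protocol 12.3.2 describes the same endpoint as a rate "per subject during the 12-month study observation period while receiving IMP", although its own w is also weeks on study.

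**Restriction to IMP.** SAP 3 and Protocol 3.1 and 3.3 limit primary and secondary efficacy analyses to the IMP Treatment Period. SAP 3 and Protocol 3.1 start that period at the first IMP administration and end it at study completion.

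**After IMP is stopped.** Protocol 8.1.1 to 8.1.3 keep subjects taken off IMP for antibody, thrombotic or hemolytic events in the study for safety assessments until the last phone call after long-term safety follow-up (LTSF). Under Protocol 7.11 they are on their standard IgG during that time.

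**The concern.** The primary test compares an SBI rate on IMP with 1 per subject per year. Weeks spent on CP or standard IgG do not belong in that rate. SAP 10.1 is the section a programmer will follow, and it gives a denominator with no start, no stop and no IMP qualifier.

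The phrase can reasonably be taken to include the wait. Protocol 3.5.1 uses total study duration to mean the waiting time plus the IMP time. SAP 9.1 does not help, because its exposure weeks are weeks on study drug, which that section takes as IMP or CP. The variable logdur in the SAP's code is not defined.

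The population definition adds to the problem. A subject who received only CP belongs to the SAP 5.1 set. That subject has zero IMP time, so an IMP-only log offset is undefined. If w is total study time, the subject enters the primary model with CP time alone.

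Replacing study time by the SAP 3 period removes the wait but leaves the end date loose. Study completion could be read as the last contact after LTSF, when the subject is no longer on IMP.

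**Working it through.** **1. Plan's own figures.** Protocol 3.5.1 gives a 36-week wait and 88 weeks in total, so IMP time is 88 − 36 = 52 weeks. SAP Table 1 (power) reproduces as Φ[(1 − μ)/√(μ(1 + φμ)/N) − 2.326]. For μ = 0.50 and N = 40:
- φ = 0: 0.50/√(0.50/40) = 4.472; 4.472 − 2.326 = 2.146; power 98.4%, as printed.
- φ = 2: 0.50/√(1.00/40) = 3.162; 3.162 − 2.326 = 0.836; power 79.8%, as printed.

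The calculation takes one year per subject and does not use w, so the power table is untouched by this point.

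**2. Literal w with only IMP-period SBIs in n.** The rate is multiplied by (IMP weeks)/(IMP weeks + waiting weeks).
- 36-week wait: 52/(52 + 36) = 52/88 = 0.59. One SBI on IMP scores 0.59 per year instead of 52 × 1/52 = 1.00.
- Minimum wait of 3 cycles, which Protocol 3.2.1 sets for subjects switched from IGSC or an investigational product:
  - 28-day cycle, LTSV at week 52: 52/(52 + 12) = 52/64 = 0.81.
  - 21-day cycle, LTSV at week 51: 51/(51 + 9) = 51/60 = 0.85.

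**3. Literal w with CP-period SBIs also in n.** The result depends on the SBI rate on CP, which the documents do not give. With a true IMP rate of 1.00, a 36-week wait and an assumed CP rate r, the pooled rate is (52 + 36r)/88:
- r = 0.1: 0.63
- r = 0.5: 0.80
- r = 1.0: 1.00

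**4. Time after IMP is stopped.** Take one 28-day subject stopped after infusion 6 for a thrombotic or hemolytic event. The stopping point is an assumption, as is 52 weeks for everyone else.
- IMP time to the LTSV: 6 × 4 = 24 weeks (Protocol 7.10 puts the LTSV 28 days after the last infusion).
- Extra time: two LTSF cycles plus about 8 weeks to the call (Protocol 7.11), 2 × 4 + 8 = 16 weeks.
- N = 40: 39 × 52 + 24 = 2052 person-weeks; with the tail, 2068; 16/2052 = 0.8%.
- N = 20: 19 × 52 + 24 = 1012 person-weeks; with the tail, 1028; 16/1012 = 1.6%.

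For antibody events the LTSF has no fixed length, so that tail cannot be computed.

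**5. Where the IMP period appears to end.** Protocol Tables 1 and 2 (projected duration) allot 52 weeks per subject to IMP, closing with the LTSV at week 51 or 52. Protocol 7.10 ties the LTSV to the last IMP infusion, and Protocol 6.2 ends the diary there. Protocol 12.5 and SAP 6.2 tie database lock to it. These all point to the LTSV, but neither SAP 3 nor SAP 10.1 says so.

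**The case against.** The strongest reply is that the intent is already clear. SAP 3 restricts the efficacy data to the IMP Treatment Period, so n and w should be cut together. The SAP introduction says it supplements the protocol, so leaving out the on-IMP qualifier in SAP 10.1 does not cancel Protocol 12.3.2. SAP 10.1 itself speaks of a 12-month period, which an 88-week denominator does not fit. On this reading the factors in step 2 describe an analysis that nobody proposes. This stands as to intent. It does not repair the text, because the formula and offset still name a different quantity, and Protocol 12.3.2 shares the same w.

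The wide set definition also has a purpose. SAP 6.1, 10.2 and 11 call for CP-period summaries, and an IMP-only set would drop CP-only subjects from them. This also stands, and it is why two sets are needed.

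A reader might go further in three ways that the documents do not support.
- **That the plan instructs CP time to be counted, so that the primary test is biased.** SAP 3 and Protocol 3.3 say the opposite.
- **That an IMP hold would put a sizeable share of CP time into the rate.** CP can be given during a hold (Protocol 8.1.1 to 8.1.3), but no hold length is stated. The review intervals in Protocol 1.4 belong to planned reviews during which treated subjects stayed on IMP.
- **That IMP-period adverse event percentages are diluted.** SAP 11.2 leaves the denominator unstated, but the number of CP-only subjects is not given and may be zero. SAP 6.1 and 11 already report by period.

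**Conclusion.** The point holds as a conflict of wording that should be corrected before the analysis is programmed. SAP 5.1 and 5.2 contradict the protocol synopsis on who is analysed. The w and offset in SAP 10.1 contradict the plan's IMP-only restriction.

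If SAP 3 governs, none of the waiting time enters and no bias arises. The factors 0.59 and 0.81 to 0.85 are per-subject figures. They apply only if w is read literally while n is confined to IMP-period SBIs. If CP-period SBIs are counted as well, the distortion depends on an unknown CP rate.

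The loose end date matters less. The protocol points to the LTSV, and one discontinued subject adds 0.8% (N=40) or 1.6% (N=20) to person-time under the assumptions in step 4. The power table is unaffected. So is the test on temporally associated adverse events, because SAP 11.1 weights by IMP infusions.

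**What to change.** 1. **SAP 5.1 and 5.2.** Define an IMP-treated set (at least one IMP infusion) for the primary analysis and all IMP-period tables, and a CP-treated set for the CP-period tables. State in SAP 6.1 or 11.2 that each period's percentages use subjects treated in that period. Align the study-product wording in Protocol 12.1.
2. **SAP 10.1 and Protocol 12.3.2.** Restore the on-IMP qualifier in SAP 10.1. Define n as SBIs with onset from the first IMP infusion to the LTSV, define w and logdur as that same interval, and exclude LTSF time. Use the same end date in SAP 3.
3. **Minor clarification.** State that any CP time during an IMP hold is handled in the same way in n and in w.

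The cost is wording only. CP and IMP infusion data are already recorded (Protocol 8.5, SAP 9.1). No new data are needed, and the sample size does not change.

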12.2 Handling of Missing Data

For the primary efficacy analysis, the method of maximum likelihood estimation will be used in conjunction with a negative binomial model to obtain a 99% one-sided upper confidence limit on the rate of serious bacterial infections. Since the resulting confidence interval leads to valid statistical inference assuming missing data are missing at random, no data imputation will be used in this analysis. With respect to safety and secondary endpoints, no data imputation will be used in the analysis of any other data from this study including the PK evaluations. Missing data will be omitted from summary statistics.

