1. INTRODUCTION

This statistical analysis plan (SAP) describes the planned data summaries and statistical analyses for Study 2004C009G, entitled “A Phase 3, Multinational, Multicenter, Open-Label Study of the Safety, Tolerability, Efficacy, and Pharmacokinetics of ProMetic BioTherapeutics Immune Globulin Intravenous (Human) 10% in Adults and Children with Primary Immunodeficiency Diseases”. It is meant to supplement the study protocol, v.5 dated 22 December 2016, which should be referred to for details regarding the objectives and design of the study. Any deviation to this SAP will be described in the clinical study report (CSR).

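### The SAP states a negative binomial model for the primary 99% upper limit, but the only code it offers fits a deviance-scaled Poisson model; the two can decide differently, and no rule covers a cohort with zero SBIs.

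*SAP*

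**What the plan says.** SAP 10.1 defines success as "a 99% one-sided (upper) confidence limit for the incidence rate of SBIs" lying below 1 per subject per year. It then states: "To calculate the confidence limit, a negative binomial regression model will be used", with an overdispersion parameter and time on study as an offset. Protocol 12.3.2 says the same, and protocol 12.2 adds that "the method of maximum likelihood estimation will be used in conjunction with a negative binomial model".

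SAP 10.1 next says "The following SAS code can be used". The model line of that code is "model count= /offset=logdur dist=poisson link=log dscale alpha = 0.02". This is the only code given for the primary endpoint; the code in SAP 11.1 serves a different one.

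The decision is taken twice: "The primary efficacy analysis will be performed using all treated population for Cohort 1 only and for Cohort 2 only". On the standing of the SAP, its Introduction says "It is meant to supplement the study protocol" and that departures from the SAP will be reported in the study report.

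Zero is mentioned in SAP 10.1 only as a row of a frequency table of SBIs per subject. Neither SAP 6.3 nor protocol 12.2 says what to report when a cohort has no SBIs.

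**The concern.** `dist=poisson` with `dscale` contains no negative binomial dispersion parameter. It fits a Poisson rate and multiplies the standard error by the square root of deviance/df. The stated model estimates the extra variance by maximum likelihood. These are different limits for the trial's sole efficacy criterion.

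Because the SAP says the code may be used, running it could be presented as following the SAP, so it need not appear as a deviation in the study report. In an open-label study, a choice between two limits should be closed before the analysis. If it stays open, data that fail under the stated model could be reported as a success.

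A second gap is separate. If a cohort has no SBIs, the estimated log rate is minus infinity and a Wald limit has nothing to be centred on.

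**Working it through.** **Inputs.** One-sided 99% limit, threshold 1 per person-year, the model text and the code (SAP 10.1). N=40 and N=20, overdispersion phi from 0 to 2, variance mu(1+phi·mu), quantile 2.326 (SAP 4). One year per subject is my assumption.

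**The plan's own figures.** Power = Phi((1−mu)·sqrt(N)/sigma − 2.326). At mu=0.50, phi=2, N=40, sigma²=0.5×2=1, so Phi(0.5×6.325−2.326)=Phi(0.836)=79.8%, as in SAP Table 1. All 20 cells reproduce within 0.1 point. The printed formula leaves out sqrt(N); the table needs it.

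**Level.** `alpha = 0.02` two-sided is a one-sided 99% limit, so the level in the code is right. Only the model differs.

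**Formulas for the limits**, with S SBIs in n subjects and m=S/n:
- Code: m·exp(2.326·sqrt((D/(n−1))/S)), where D=2·Σ y·ln(y/m).
- Negative binomial (NB): m·exp(2.326·sqrt((1+phi_hat·m)/S)), where phi_hat is the maximum likelihood estimate, at least 0.
- Exact Poisson: chi²(0.99; 2(S+1))/(2n).

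**An opposite decision.** N=40, 20 SBIs: 6 subjects with 1, 2 with 2, 2 with 3, 1 with 4, so m=0.5.
- Code: D=57.54 and D/39=1.476. The limit is 0.5·exp(2.326·sqrt(1.476/20)) = **0.941**, success.
- NB: phi_hat=2.43. The limit is 0.5·exp(2.326·sqrt(2.215/20)) = **1.084**, failure.

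A second data set, 18 SBIs in 40 (4 subjects with 1, 2 with 2, 1 with 4, 1 with 6), gives 0.923 and 1.263.

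**How often** (simulated gamma-Poisson trials):

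| mu, N | phi | only the code succeeds |
|---|---|---|
| 0.5, 40 | 2 | about 16% |
| 0.5, 40 | 1 | 9–10% |
| 0.5, 40 | 0.5 | 5% |
| 0.5, 40 | 0 | 1.4% (reverse about as common) |
| 0.4, 20 | 2 | about 16% |

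**False success at a true rate of 1** (nominal 1%). At phi=2 it is 3.4% for the code against 1.9% for NB (N=40), and about 4% against 2.8% (N=20). At phi=0.5 and 1 the code exceeds NB by only about 0 to 0.6 points. At phi=0 both are below 1%.

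**Few SBIs.** One SBI in 40: D=2·ln(40)=7.38 and D/39=0.189, so the scaling shrinks the standard error below the Poisson value. The code gives 0.069, NB 0.256 and exact Poisson 13.28/80=0.166. The coded limit is too low, but all three are far below 1.

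**Few SBIs in one subject.** Two SBIs in one subject give 0.138 (code), 1.037 (NB) and 0.210 (exact) at N=40, and 0.369, 1.967 and 0.420 at N=20.

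**Zero SBIs.** Neither model gives a usable Wald limit, and a trial Poisson fit in standard software failed. The exact Poisson limit is −ln(0.01)/T = 4.605/T, which is 0.092, 0.115, 0.184 and 0.230 for 50, 40, 25 and 20 subject-years. At an assumed rate of 0.10 without overdispersion, zero SBIs has chance exp(−2.5)=8% in 25 subject-years and exp(−5)=0.7% in 50. At the plan's 0.40 or more it is 0.3% or less unless counts are overdispersed; at mu=0.4, phi=2, N=20 it was again 0.3% in simulation.

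**The case against.** The best reply is that nothing is truly ambiguous. Both documents say a negative binomial model will be used, the code is only optional, and the SAP supplements the protocol. Harm then needs an analyst to follow optional code against mandatory text. As a reading of which method governs, this stands. It does not dispose of the point, because the SAP itself authorises the code and contains no precedence statement.

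Three further objections limit the point:
- The excess of false success is clear only at phi=2, the extreme of the plan's grid, and NB is itself above 1% there. A reader might infer that the code generally inflates the error rate. The calculations at phi=0 to 1 do not show that.
- The flips with two or three SBIs in one subject need phi_hat of about 23 to 92, far outside the planned 0 to 2. NB limits of 1.0 to 2.0 beside exact limits of 0.2 to 0.4 show instability of the NB Wald limit as much as a fault in the code.
- A reader might infer that a zero-SBI cohort would pass spuriously. It would not: the exact limits are 0.092 to 0.230, so success is the right decision. What is missing is a reportable limit.

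**Conclusion.** The point holds. The stated model and the permitted code are different methods, and the code is mostly the more lenient one when counts are overdispersed. At mu=0.5, N=40 the share of trials in which only the code succeeds runs from about 16% at phi=2 to 1.4% at phi=0, where it is balanced by the reverse. With few, unclustered SBIs the decision is the same and only the reported limit is wrong. The missing zero-SBI rule is a reporting gap that matters if the true rate is well below the planning range.

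It would go too far to say that the sponsor intends the Poisson analysis; the text in both documents points the other way. Because this limit is the only efficacy criterion, applied separately to adults and children, the mismatch must be corrected before analysis.

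The figures rest on one year per subject, Wald limits on the log scale with maximum likelihood dispersion, and gamma-Poisson simulation. SAS itself was not run.

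**What to change.** In SAP 10.1:
1. Replace `dist=poisson` and `dscale` with `dist=negbin` and no scale option, and state that the negative binomial model governs. If the sponsor prefers a scaled method, it should instead amend the model text in both protocol and SAP and justify the choice before analysis, with the scale not allowed to fall below 1.
2. Add: *If a cohort has zero SBIs or the negative binomial fit does not converge, the exact Poisson one-sided 99% upper limit on total person-years is reported.*

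The edits are small, but the first has a real cost. At mu=0.5, phi=2, N=40 the chance of success is about 49% with NB against 64% with the code, while the power table shows 79.8%. At phi=0 both are about 85%. The gain in error control is partial, since NB limits still exceed the nominal 1% at phi=2. A few SBIs in one subject can also push the NB limit above 1 at a low observed rate, and the fallback does not apply there because the fit converges. The sponsor should weigh that when choosing between the two routes in item 1.
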